6.11 Concomitant therapy

6.11.1 Prohibited

During the course of the study, experimental medications for MCI or AD and all other experimental medications are prohibited. Subject must refrain from using any medication, vitamin, or herbal supplement considered to enhance cognition or indicated for a-MCI or AD unless approved by the investigator. Prohibited medications, vitamins and herbal supplement included but are not limited to cholinesterase inhibitors, memantine, Axona, ginko biloba, and huperzine.

6.11.1 Permitted

Concomitant medications will be assessed at all study visits. Concomitant medications are prescribed or over-the-counter medications and should be consistent with the inclusion/exclusion criteria. Concomitant medication appropriate to the subject's condition may be prescribed during the course of the study with the exception of those listed above.

Routine vaccinations (i.e., flu vaccination) with commercially available therapeutics are permitted but must not be given within four weeks before or after the administration of the study drug. No vaccination for a-MCI or AD is allowed during the course of the study.

7.0 EVALUATIONS BY VISIT

The overall summary of study activities by visit is provided in Appendix C at the end of the document.

Screening procedures at visit 1 will take place up to 28 days prior to Visit 2 (Day 1) dosing. Screening labs and assessments will be performed during the screening period. A brain MRI will be obtained as standard of care within 6 months prior to the screening period. The first dose of study drug is administered on Day 1. Visits 2 through 6 have a ± 1 day window and occur every 14 days over two months. The investigator will determine if a subject is suitable to continue following the missed infusion. Visits 7 through 12 (Month 4 through Month 24) have a ± 7 day window. Visits 13 through 15 (Month 36 through Month 60) have a ± 14 day window).

All study screening data from Visit 1 including laboratory results must be reviewed for study eligibility prior to receiving first dose of study drug. Visit 2 physical exams and neurological exams prior to infusion may occur within 72 hours prior to the first infusion. Prior to infusion, a review of concomitant medications and AEs takes place to ensure that no excluded medications have been added or medication discontinued or dose changed that were required to have been stable. If the subject continues to be eligible for enrollment, the subject will be randomized, infused with study medication and will remain in the infusion clinic for at least 4 hours following the start of the infusion for safety assessments on Visit 2 (Day 1).

7.1 VISIT 1: Screening

The following screening procedures will occur up to 28 days prior to Visit 2 (Day 1) infusion:

- Obtain signed and dated SHCIRC approved written Informed Consent from the subject and collaborative informant prior to the initiation of any screening procedure
- Assess Inclusion/Exclusion criteria
- Obtain medical history
- Record prior medications
- Assess Petersen criteria for mild cognitive impairment
- Determine Rosen Modified Hachinski Ischemic score
- Record vital signs
- Perform physical examination including height and weight
- Perform neurological examination
- Obtain standard 12-lead ECG
- Obtain a brain MRI according to Appendix E for clinical assessment, ventricular volume, and review the scan for evidence of vasogenic edema, microhemorrhage, infarction or other clinically significant abnormality
- Perform lumbar puncture to obtain CSF A β 1-42/CSF P-Tau_{181P}
- Administer MMSE, ADAS-Cog, and CDR-SB
- Obtain blood sample for ApoE genotyping, IgA deficiency, serum viscosity

- Obtain blood sample for complete blood count (CBC) and comprehensive metabolic panel (chemistry panel). (Appendix D)
- Obtain blood sample for thyroid stimulating hormone (TSH), vitamin-B12 and rapid plasma reagin laboratory tests
- Obtain blood sample for HIV-I & II, HCV, HBV, B19, HAV
- Obtain urine sample for routine urinalysis

7.2 VISIT 2: Day 1 – First Infusion

The investigator will confirm that subjects are still eligible by reviewing all screening data. Subjects who no longer meet criteria will not be eligible for enrollment in the study.

7.2.1 Pre-dose:

- Confirm that subjects continue to meet inclusion/exclusion criteria
- Assess and record AEs
- Record concomitant medications
- Record vital signs
- Perform physical and neurological examinations (may occur within 72 hours prior to first infusion)
- Complete randomization
- The unblinded pharmacist will prepare the study drug according to the preparation instructions in Section 5.7 and will deliver the study drug to the blinded infusion administration site.

7.2.2 Study drug infusion:

- Subjects will be given the option of prophylaxis oral acetaminophen, diphenhydramine, or both 15-30 minutes prior to infusion
- Measure blood pressure, pulse rate, temperature and respiratory rate within 15 minutes prior to start of the infusion
- Administer study drug to the subject by intravenous infusion

7.2.3 Following initiation of infusion:

- Measure blood pressure and pulse rate at 15, 30, 60 and every 30 minute mark for the duration of the infusion
- Measure blood pressure, pulse rate, temperature and respiratory rate immediately post dose and prior to leaving the clinic
- Assess infusion site post infusion
- Assess and record AEs
- Subjects will remain in the clinic for at least one hour following the completion of the infusion. The subjects may leave the clinic after the observation period if the subject is medically stable.

7.3 VISIT 3 (Day 14 -Second Infusion) through VISIT 6 (Day 56 – Fifth Infusion)

- Assess and record AEs
- Record concomitant medications
- Record vital signs
- If there is any abnormality of vital signs or clinical concerns during infusion visit, the principle-investigator or sub-investigator will be paged in order to perform a clinical assessment.
- The unblinded pharmacist will prepare the study drug according to the preparation instructions and will deliver the study drug to the blinded infusion administration

7.3.1 Study drug infusion:

- Subjects will be given the option of prophylaxis oral acetaminophen, diphenhydramine, or both 15-30 minutes prior to infusion
- Measure blood pressure, pulse rate, temperature and respiratory rate within 15 minutes prior to start of the infusion
- Administer study drug to the subject by intravenous infusion

7.3.2 Following initiation of infusion:

- Measure blood pressure and pulse rate at 15, 30, 60 and every 30 minute mark for the duration of the infusion
- Measure blood pressure, pulse rate, temperature and respiratory rate immediately post infusion and prior to leaving the clinic
- Assess infusion site post infusion
- Assess and record AEs
- Subjects will remain in the clinic for at least 15 minutes following the completion of the infusion. The subjects may leave the clinic after the observation period if the subject is medically stable.

7.4 VISIT 7: Month 4 (±7 days)

- Assess and record AEs
- Record concomitant medications
- Record vital signs
- Perform physical and neurological examinations
- Record vital signs
- Assess and record AEs
- Record concomitant medications
- Obtain standard 12-lead ECG
- Administer MMSE, ADAS-Cog, and CDR-SB
- Obtain blood sample for routine hematology and chemistry laboratory tests
- Obtain blood sample for HIV-I & II, HCV, HBV, B19, HAV

7.5 VISIT 8: Month 8 (± 7 days)

- Assess and record AEs
- Record concomitant medications
- Record vital signs
- Perform physical and neurological examinations
- Administer MMSE, ADAS-Cog, and CDR-SB
- Obtain blood sample for HIV-I & II, HCV, HBV, B19, HAV

7.6 VISIT 9: Month 12 (± 7 days) - 12 months after baseline

- Assess and record AEs
- Record concomitant medications
- Record vital signs
- Obtain a brain MRI according to Appendix E for clinical assessment, ventricular volume, and review the scan for evidence of vasogenic edema, microhemorrhage, infarction or other clinically significant abnormality
- Perform physical and neurological examinations
- Administer MMSE, ADAS-Cog, and CDR-SB
- Obtain blood sample for routine hematology and chemistry laboratory tests

7.7 VISIT 10: Month 16 (± 7 days)

- Assess and record AEs
- Record concomitant medications
- Record vital signs
- Perform physical and neurological examinations
- Administer MMSE, ADAS-Cog, and CDR-SB

7.8 VISIT 11: Month 20 (± 7 days)

- Assess and record AEs
- Record concomitant medications
- Record vital signs
- Perform physical and neurological examinations
- Administer MMSE, ADAS-Cog, and CDR-SB

7.9 VISIT 12: Month 24 (± 7 days) - 24 months after baseline

- Assess and record AEs
- Record concomitant medications
- Record vital signs
- Perform physical and neurological examinations
- Obtain standard 12-lead ECG
- Obtain a brain MRI according to Appendix E for clinical assessment, ventricular volume,

and review the scan for evidence of vasogenic edema, microhemorrhage, infarction or other clinically significant abnormality

- Administer MMSE, ADAS-Cog, and CDR-SB
- Obtain blood sample for routine hematology and chemistry laboratory tests

7.10 VISIT 13: Month 36 (±14 days) – 36 months after baseline (extension visit)

- Assess and record AEs
- Record concomitant medications
- Record vital signs
- Perform physical and neurological examinations
- Obtain a brain MRI according to Appendix E for clinical assessment, ventricular volume, and review the scan for evidence of vasogenic edema, microhemorrhage, infarction or other clinically significant abnormality
- Administer MMSE, ADAS-Cog, and CDR-SB

7.11 VISIT 14: Month 48 (±14 days) – 48 months after baseline (extension visit)

- Assess and record AEs
- Record concomitant medications
- Record vital signs
- Perform physical and neurological examinations
- Obtain a brain MRI according to Appendix E for clinical assessment, ventricular volume, and review the scan for evidence of vasogenic edema, microhemorrhage, infarction or other clinically significant abnormality
- Administer MMSE, ADAS-Cog, and CDR-SB

7.12 VISIT 15: Month 60 (±14 days) – 60 months after baseline (extension visit)

- Assess and record AEs
- Record concomitant medications
- Record vital signs
- Perform physical and neurological examinations
- Obtain a brain MRI according to Appendix E for clinical assessment, ventricular volume, and review the scan for evidence of vasogenic edema, microhemorrhage, infarction or other clinically significant abnormality
- Administer MMSE, ADAS-Cog, and CDR-SB

7.13 Early termination from the study

Every attempt should be made to follow each subject through the final visit 12, and subsequently visit 15 of the extension study. In the event of early withdrawal from the subject for any reason, an Early Termination Visit should be completed for criteria of withdrawal. If the subject withdraws due to an AE, every attempt should be made to follow the subject until the AE resolves or until the investigator deems that the AE is stable or determined the AE to be chronic. All SAEs will continue to be followed until the end of the study (Visit 12, 15, or ET visit) or until the SAE has resolved or the investigator deems the event to be stable or chronic.

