 1. HIV-I & II, HCV, HBV, B19, HAV
 2. Adverse events and Concomitant Meds
- Complete all Visit 9 study activities described above
- Subjects will not attend Visit 10 and Visit 11
- Complete all Visit 12 study activities
- Complete all Visit 13, 14, and 15 study activities (optional)

Patients who convert to Alzheimer Disease will be followed for safety reasons, to determine rate of conversion between groups, and to track any continued changes in ventricular volume between the 0.4 g/kg NewGam or 0.9% saline solution (placebo) groups.

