10.2 Serious adverse event (SAE) definition

A serious adverse event is one that at any dose (including overdose):

- Results in death
- Is life-threatening¹
- Requires inpatient hospitalization or prolongation of existing hospitalization
- Results in persistent or significant disability or incapacity²
- Is a congenital anomaly/birth defect
- Is a medically important condition:
 - Suspected transmission of an infectious agent,
 - Thromboembolic events,
 - Cerebral hemorrhage resulting in clinical disability, or
 - Other reactions that should be reported in an expedited manner although they did not immediately result in one of the above seriousness criteria

10.3 Other relevant drug safety information:

Any safety information relating to

- Pregnancies/breastfeeding,
- Drug abuse (persistent, sporadic or intentional excessive use of a medicinal product inconsistent with the SPC or acceptable medical practice),
- Overdose (treatment exceeding the medically recommended dose),
- Medication errors (prescribing or dispensing error),
- Interactions with other medicinal products or devices
- Associated with NewGam 10%, even if no adverse drug reaction occurred.

¹"Life-threatening" means that the subject was at immediate risk of death at the time of the serious adverse event; it does not refer to a serious adverse event that hypothetically might have caused death if it were more severe.

²"Persistent or significant disability or incapacity" means that there is a substantial disruption of a person's ability to carry out normal life functions.

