22.0 APPENDIX C

22.1 Schedule of study activities

Study Visit	1	2	3	4	5	6	7	8	9	10	11	12	13	14	15
Study Time Point	Day -28 To Day -1	D1	D14	D28	D42	D56	M4	M8	M12	M16	M20	M24 /ET ⁶	M36	M48	M60 /ET ⁷
Visit Type (Visit Window)	Screening	Infusion Visits (±1 day)					Follow-up (±7 days)					Follow-up (±14 days)			
CLINICAL															
Informed consent	X														
Inclusion/Exclusion	X	X													
Medical Hx/Prior/Baseline Medications	X														
a-MCI Petersen/NIA criteria review	X														
Modified Hachinski Ischemia Scale	X														
ApoE4 genotyping ¹	X														
Vital Signs	X	X	X	X	X	X	X	X	X	X	X	X	X	X	X
Physical Exam	X	√ ²					X	X	X	X	X	X	X	X	X
Neurological Exam	X	√ ²					X	X	X	X	X	X	X	X	X
ECG	X						X					X			
Brain MRI	X								X			X	X	X	X
CSF-amyloid protein 1-42 tau 181P biomarker mixture (Optional)	X														
Mini Mental State Exam (MMSE)	X						X	X	X	X	X	X	X	X	X
CDR-SB, ADAS-cog	X						X	X	X	X	X	X	X	X	X
HIV-I & II, HCV, HBV, B19 ³ , HAV ³	X						X	X							
IGA deficiency	X														
Serum viscosity	X														
CBC, Chemistry Panel (Appendix B)	X						X		X			X			
TSH, Vit-B12, RPR ⁴	X														
Urinalysis ⁵	X														
Adverse events & Concomitant Meds		X	X	X	X	X	X	X	X	X	X	X	X	X	X

Study Visit	1	2	3	4	5	6	7	8	9	10	11	12	13	14	15
Study Time Point	Day -28 To Day -1	D1	D14	D28	D42	D56	M4	M8	M12	M16	M20	M24/ ET ⁶	M36	M48	M60 /ET ⁷
Visit Type (Visit Window)	Screening	Infusion Visits (±1 day)					Follow-up (±7 days)					Follow-up (±14 days)			
THERAPY															
Randomization		X													
Infusion of IVIG or placebo		X	X	X	X	X									
Assess infusion site		X	X	X	X	X									
¹ Previous ApoE4 testing will be accepted				⁴ RPR required if not done in the last 12 months prior to screening											
² Exams may occur within 72 prior to infusion				⁵ Urine culture may be performed if indicated											
³ Performed at 4 and 8 months only if subject is negative at baseline				⁶ Early Termination visit for subjects in the two study (Section 7.13)											
				⁷ Early Termination visit for subjects in the three year extension study (Section 7.13)											

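### The Early Termination visit has no viral panel, so an infused subject who leaves before Month 4 or Month 8 has none or only one of the two planned post-infusion panels scheduled

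*Combined protocol and SAP*

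**What the plan says.** Section 7.13 triggers the visit: "In the event of early withdrawal from the subject for any reason, an Early Termination Visit should be completed for criteria of withdrawal". It gives no list of assessments. Appendix C (22.1) supplies the content by placing ET in the Month 24 column, with the footnote "Early Termination visit for subjects in the two study (Section 7.13", and in the Month 60 column for the extension.

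The Appendix C row "HIV-I & II, HCV, HBV, B19 ³ , HAV ³" is marked at Visits 1, 7 and 8 only. Its footnote for B19 and HAV reads "Performed at 4 and 8 months only if subject is negative at baseline". The visit text agrees: 7.4 (Month 4) and 7.5 (Month 8) both include "Obtain blood sample for HIV-I & II, HCV, HBV, B19, HAV", while the only blood test in 7.9 (Month 24) is "Obtain blood sample for routine hematology and chemistry laboratory tests".

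Three other sections bear on the point:

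- Section 8.0 reduces a converter's Visit 8 to two items: "HIV-I & II, HCV, HBV, B19, HAV", and the review of adverse events and concomitant medications.
- Section 10.2 names "Suspected transmission of an infectious agent" among the medically important conditions that count as serious adverse events.
- Section 9.2 says that subjects withdrawn once they have had the third infusion are not replaced, but are followed up if they agree.

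**The concern.** The Month 24 list suits a subject who completes two years, because both post-infusion panels are already done. The same list is applied to a subject who leaves in the infusion period or soon after, when one or both panels are still to come. A site that followed Appendix C to the letter would obtain an MRI, an ECG, cognitive tests and routine bloods from that subject, and would not draw the panel the protocol uses to look for transmitted infection after a human plasma product.

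The matter at stake is participant safety follow-up. Under 10.1, adverse event collection ends at the ET visit, so nothing scheduled after it would pick up an infection without symptoms.

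**Working it through.** The plan states no figure on this point, so the check sets the schedule against the text.

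**1. Is the blank cell real?** The viral, CBC/chemistry, ECG and MRI rows of Appendix C each split into a label and 15 visit cells.

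| Row | Visits marked |
|---|---|
| Viral panel | 1, 7 (M4), 8 (M8) |
| CBC/chemistry | 1, 7 (M4), 9 (M12), 12 (M24/ET) |
| ECG | 1, 7 (M4), 12 (M24/ET) |
| MRI | 1, 9 (M12), 12 (M24/ET), 13, 14, 15 (M60/ET) |

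The last three rows match the visit-by-visit text of section 7, so the columns are correctly aligned. The viral row also matches 7.1, 7.4, 7.5 and 7.9. The blank under ET is in the plan and is not a fault of the table.

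**2. Which ET column matters?** The Month 60 column applies only to subjects in the extension, who are past Month 8, so its blank does no harm. The gap lies in the Month 24 column.

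**3. Post-infusion panels scheduled, by time of leaving.**

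| Infused subject leaves | Month 4 | Month 8 | At ET | Scheduled |
|---|---|---|---|---|
| Before Month 4 | missed | missed | none | 0 of 2 |
| Between Months 4 and 8 | done | missed | none | 1 of 2 |
| After Month 8 | done | done | none | 2 of 2 |

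**4. Can a fully dosed subject fall in the first row?** The fifth infusion is on Day 56 (7.3). Taking 30.44 days per month, Month 4 is 4 × 30.44 ≈ Day 122. The first re-test comes 122 − 56 = 66 days after the last infusion, or 59 to 73 days with the ±7-day window. A subject can therefore have one to five infusions and leave with no re-test scheduled.

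**5. Effect of section 9.2.**

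- One or two infusions: 9.2 promises no follow-up, so the gap stands.
- Three to five infusions, with consent: the subject can still reach the remaining Month 4 and Month 8 draws.
- Three to five infusions, without consent: the gap stands.

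**6. Number affected.** No dropout rate is given. As an assumption only, if 5% to 15% of the 25 IVIG subjects left before Month 8, then 0.05 × 25 = 1.25 to 0.15 × 25 = 3.75 recipients would lack one or both panels, before any allowance for consented follow-up. Across both blinded arms the range is 0.05 × 50 = 2.5 to 0.15 × 50 = 7.5. The group leaving before Month 4, with no panel at all, can only be the same size or smaller.

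**The case against.** The strongest reply is that the gap is narrower than the schedule suggests. Section 7.13 asks sites to try to keep every subject to Visit 12 and to follow those who leave because of an adverse event, and 9.2 offers consented follow-up after the third infusion. An investigator may also order serology at any time. All of this stands. A reader might infer that early leavers are never re-tested. The documents show only that no re-test is scheduled or required. The gap remains because the request in 7.13 does not bind a subject who leaves, its adverse event follow-up concerns events already known, and 9.2 is silent on subjects withdrawn before the third infusion.

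A second reply is that 10.2 is a reporting definition for suspected transmission and does not call for serology. That is correct. The firmer comparison is with 8.0, which keeps the panel when almost everything else at Visit 8 is dropped. Even that concerns subjects who stay in the study, so it shows the weight given to the panel and does not set a rule for leavers.

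A reader might also infer that the trial's conclusion on viral safety would be biased towards those who stayed, or that those leaving because of an adverse event are the ones whose viral status matters most. The documents support neither. No seroconversion analysis is planned, 15.2.2 evaluates safety through recorded adverse events, and nothing ranks leavers by viral risk.

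Finally, a draw at an arbitrary ET date, perhaps days after an infusion, may say little, and the protocol chose Months 4 and 8. That is a fair reason to leave timing open and to allow a return visit, but not to leave the ET entry blank.

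**Conclusion.** The point holds as a gap in the safety schedule. Appendix C applies a completer's list to early leavers, and 7.13 does nothing to correct it. Unless 9.2 applies and the subject consents, an infused subject has 0 of 2 post-infusion panels scheduled if leaving before Month 4, and 1 of 2 if leaving between Months 4 and 8. This sits poorly with 8.0 and with the naming of suspected transmission in 10.2.

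The reading rests on Appendix C being the only definition of the ET visit, and no other section supplies one. The number of subjects is probably small in a trial of 50 but cannot be known from the documents; the range of about 1 to 4 IVIG recipients depends on an assumed dropout rate and covers all departures before Month 8. No efficacy analysis is affected. The correction should be made because it concerns participant safety and costs little.

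**What to change.** Reconcile 7.13, 9.2 and Appendix C:

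- Give Early Termination its own entry in place of sharing the Month 24 column, and refer to it from 7.13.
- State in that entry that infused subjects who leave before Visit 8 are covered by the existing viral panel, at the ET visit, by a consented return for the remaining Month 4 or Month 8 draw, or both. The sponsor and investigator should set the timing.
- Say in 9.2 what follow-up is offered to subjects withdrawn before the third infusion, and whether follow-up after the third infusion includes these draws.
- Report, by arm, how many infused subjects lack one or both post-infusion panels.

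The cost is a few lines of text and, for a few early leavers, one extra tube at a visit where blood is already taken or an optional return visit. The assay is already in use in the study. The rationale for Amendment 8 refers to conversions by year 2, so for subjects past Month 8 a change to the schedule comes too late; the count can still be reported for them.

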8.0 CONVERSION TO ALZHEIMER DISEASE

Patients who convert to AD will have the choice of remaining in the study on a modified follow-up visit schedule, or may withdraw from the study. Depending on when the conversion occurs, the subjects will be asked to complete the following:

- Complete all Visit 7 study activities described above
- Complete only the following for Visit 8:
